Achieving a comfortable and functional connection between an amputee and their prosthetic limb is critical to the success of the prosthesis. Therefore, the socket system is the most significant component for overall success of the prosthesis^{1,2}. In an effort to maximize socket performance and comfort without adversely affecting residual limb health, a prosthetist custom fits a socket for every patient using plaster wraps or computer aided design. Currently, this process suffers from a lack of quantitative feedback to determine appropriate socket fit. Prosthetists aim to minimize suspension-dependent movement between the socket and residual limb, but current approaches are limited as they rely on anecdotal visual cues along with subjective verbal feedback from the patient. Prosthetists then use this information to revise socket parameters such as volume, geometry, and type of suspension to provide current 'best' fit for a patient. Regardless of prosthetist fitting, the volume of mature residual limb (>18 months post-amputation³) are subject to daily⁴ and chronic^{5,6} changes in volume that compromise socket fit and performance. For the 1 million Americans that live with a lower-limb amputation, a growing number of which are service men and women⁷⁻⁹, these volume changes adversely affect fit, performance, and residual limb health⁶ – including skin breakdown and ulceration¹⁰ that can necessitate revision of the amputation. Indeed, for traumatic lower-limb amputations, the requirement for surgical revision is known to be as high as 30%¹¹.

II. Objective:

Aim 1 will evaluate the relationship between vacuum pressure and limb movement inside the socket and how it changes with respect to vacuum pressure setting, gait speed and socket volume

Aim 2 will evaluate the impact of socket movement on residual limb circulation and residual limb skin health

Aim 3 will compare the effectiveness of an adaptive vacuum system to standard of care suspension prosthetics (pin-locking or suction).

Study Population: Up to 170 amputees will be enrolled in the study overall.

1. **Aim 1:** 10 trans-femoral amputees and 10 trans-tibial amputees will be enrolled.
2. **Aim 2:** 15 trans-tibial and 15 trans-femoral amputees will be enrolled.
3. **Aim 3:** n=120 (trans-tibial and trans-femoral amputees) will be enrolled.

III. Inclusion Criteria:

1. Ages of 18 and above

2. Unilateral trans-tibial or trans-femoral amputee
3. Ambulate at a K2 level or higher

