We are requesting the use of ResearchMatch.org for subject recruitment on this protocol. See attached General Description of ResearchMatch attached.

Descriptions of prosthesis suspension platforms:

Pin-locking prosthesis: A gel-liner with an attached pin, lanyard, KISS system that clicks into a locking mechanism (receiver) inside the socket.

Suction prosthesis: A total contact weight bearing socket with a one-way expulsion valve to let air out.

Adaptive vacuum test prosthesis (“test” system): The adaptive vacuum prosthesis is sold as a commercial device by the company Willow Wood with suggested U.S. L-Code L5781. The device is designated as a Class 1 Medical Device and 510(K) Exempt. This category is part of a low or moderate risk to patient safety and health. The Prosthetic socket system uses an active vacuum pump to push air out of the socket. The level of vacuum is controlled by hardware that automatically detects the socket fit based on in-socket motion and adjusts vacuum as needed to eliminate this motion.

VI. Aim 1 (Completed):

1. **Study Visit 1** This initial visit will take place at The Ohio Willow Wood and the following research activities will take place:
 - Informed Consent will be obtained
 - Baseline demographics, medical history, and medications will be recorded
 - Verify fit of the thermoplastic socket
 - Subject will perform multiple ambulation trials at controlled cadences while the vacuum pump is set turned off (0 inHg), 7 inHg, 10 inHg, 13 inHg, and 20 inHg.
 - Subject will repeat the ambulation task with different thickness liners to simulate global volume changes.
 - Subject will repeat the ambulation task with a gel pad insert to simulate local volume changes.

VII. Aim 2 (partially completed if additional subjects are needed, they will be recruited at OWW with their approved IRB protocol):

1. **Study Visit 1 (Baseline)** This initial visit will take place at OSUWMC & OWW where the following research activities will take place:
 - Informed Consent will be obtained

- Baseline demographics, medical history, and medications will be recorded
- Subjects will perform seated tasks, standing tasks, and walking on a treadmill task. Skin health measurements will be taken before and after the activity period.
- Hyperspectral Imaging – A non-invasive visible light imaging technology will measure tissue oxygenation

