All subjects will be compensated \$100 for each of the completed visits. Aim 1 subjects will be compensated \$100 for the completed study visit 1. Aim 2 subjects will have 4 total visits and will be eligible for a maximum of \$400 for completion of all study visits. Aim 3 subjects will have 3 total visits and will be eligible for a maximum of \$450 for the completion of all visits per following schedule: Visit #1 (\$50), Visit #2A & B (\$150, for completing all socket fitting activities

& baseline) and Visit #3A&B (\$250). Subjects will not be paid if any of study visits are not completed.

XV. Statistical Analysis:

Patient demographics and clinical characteristics will be described using frequencies and percentages for categorical data and median and the interquartile range (IQR) for continuous data. In Aim 1, random-effects linear regression will be used to assess the relationship between wave amplitude and distal movement (or lateral shift) controlling for vacuum pressure. Patient ID will be the random-term in the model. In Aim 2, random-effects linear regression will also be used to compare percent change in limb perfusion across adaptive EVS and suction at 12 weeks controlling vacuum pressure and controlling for the baseline EVS and suction values. In Aim 3, a random-effects linear regression model will be used to establish the relationship in amputee performance (as measured by the CHAMP tasks) and residual limb health across EVS and suction and across EVS and pin-locking/lanyard in a cross-over design. The model includes terms for group (EVS vs. suction or EVS vs. pin-locking/lanyard), sequence (EVS to suction vs. suction to EVS or EVS to pin-locking/lanyard vs. pin-locking/lanyard to EVS), and visit (second vs. first). All statistical models will account for the effect of age, diabetes status and smoking history by including them as the covariates in the models. As per need, subjects may be stratified based upon diabetes status and arterial blood flow status. The *p*-values produced in the study will be adjusted using the Holms procedure to control the overall type I error at 0.05 due to the multiple comparisons. All analyses will be run using Stata 13.1, Stata Corporation, College Station, Texas.

XVI. References:

1. Lake, C. The evolution of upper limb prosthetic socket design. *Journal of Prosthetics and Orthotics* 20, 85 (2008).

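### The stated Aim 1 model has no gait-speed, socket-volume or interaction term, so run as written it does not estimate how the vacuum-pressure/limb-movement relationship changes

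*Combined protocol and SAP*

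**What the plan says.** Section II sets the objective in two parts. The first is a relationship: "Aim 1 will evaluate the relationship between vacuum pressure and limb movement inside the socket". The second is its modification: "how it changes with respect to vacuum pressure setting, gait speed and socket volume".

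Section VI describes one visit that sets these conditions within each patient:

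- Gait speed: "Subject will perform multiple ambulation trials at controlled cadences".
- Vacuum, at five settings: "vacuum pump is set turned off (0 inHg), 7 inHg, 10 inHg, 13 inHg, and 20 inHg".
- Global socket volume: "Subject will repeat the ambulation task with different thickness liners to simulate global volume changes".
- Local socket volume: "Subject will repeat the ambulation task with a gel pad insert to simulate local volume changes".

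Section XV gives one Aim 1 model. It is a random-effects linear regression to "assess the relationship between wave amplitude and distal movement (or lateral shift) controlling for vacuum pressure", with patient identity as the random term. All models in the section also carry age, diabetes and smoking as covariates. Optional stratification is by diabetes and arterial blood flow, and p-values are adjusted by the Holm procedure.

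Wave amplitude is not defined. The device description in section V says that the hardware "automatically detects the socket fit based on in-socket motion", so wave amplitude may be a signal from inside the socket, but that is inference.

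**The concern.** The second half of the objective is a question of effect modification with three named modifiers, and the visit appears built to answer it. The stated model contains one modifier (vacuum setting), as an adjustment only, and omits the other two. Adjusting for a factor removes its contribution to the outcome. It does not show whether the slope of interest differs across that factor's levels.

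If the analysis follows the text, the liner, gel-pad and cadence trials go into one pooled coefficient, and the report has nothing to quote on how the relationship changes. Pooling can also distort the one coefficient that is reported, because cadence and socket volume may shift both wave amplitude and movement.

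**Working it through.** No sample-size, power or effect-size figure is given for Aim 1, so there is none to reproduce. The check compares the objective, the visit and the model term by term.

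**Step 1. Count the terms.**

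| Factor in the objective (II) | Varied at the visit (VI) | Main effect in the model (XV) | Interaction in the model (XV) |
|---|---|---|---|
| Vacuum setting | Yes, 5 levels | Yes, as adjustment | No |
| Gait speed | Yes, by cadence; number of levels not stated | No | No |
| Socket volume | Yes, by liners and gel pad; number of liners not stated | No | No |

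Two of 3 factors have no term, and 0 of 3 has an interaction.

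**Step 2. Look for the terms elsewhere.** Age, diabetes and smoking are fixed for a patient within a single visit, so they cannot stand in for conditions that vary within the patient. The optional stratification is by patient characteristics too. No section plans separate fits by cadence, liner or gel pad.

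**Step 3. Write the model out.** For patient i and trial j, with movement Y, wave amplitude A and vacuum V:

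Y_ij = b0 + b1·A_ij + b2·V_ij + (patient covariates) + u_i + e_ij

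The slope on A is b1 in every condition. No parameter represents a change in it with setting, cadence or volume.

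- If wave amplitude measures vacuum pressure, b1 is the relationship of interest and is held constant by construction.
- If it does not, the objective's predictor appears only as b2, an adjustment term that is also constant across cadence and volume.

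The gap holds either way.

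**Step 4. What b1 estimates when conditions are left out.** Setting aside vacuum and differences between patients, the pooled slope is

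b1 = λ·b_within + (1 − λ)·b_between

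Here λ is the share of the variation in A that lies within cadence-and-volume conditions. b_within is the slope inside conditions (itself a weighted mean if slopes differ), and b_between is the slope across condition means. The pooled slope equals the within-condition slope only if λ = 1 or the two slopes agree. In general, then, it is not a plain average of the condition-specific slopes.

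**Step 5. Could the design carry the missing terms?** The documents do not give the numbers of cadences or volume conditions, or say whether they were crossed. As an illustration only, assume full crossing, 2 to 3 cadences and 3 to 4 volume conditions, with vacuum entered linearly.

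- Rows: from 20 × 5 × 2 × 3 = 600 to 20 × 5 × 3 × 4 = 1,200.
- Fixed coefficients, covariates aside: 3 as written. With A interacting with vacuum, S cadences and K volume conditions, 2 × [1 + 1 + (S − 1) + (K − 1)], which is 10 for S = 2, K = 3 and 14 for S = 3, K = 4.

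In data simulated on those layouts with slopes set to differ, the model as written returned a single slope of about 0.99. The interaction model recovered the assumed changes: 0.48 to 0.53 per cadence step (set at 0.5), 0.39 to 0.43 per volume step (set at 0.4) and about −0.03 per inHg (set at −0.03). This shows only that the terms are estimable if conditions were crossed and recorded. It says nothing about precision in the trial.

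**The case against.** The strongest reply is that one sentence on Aim 1 is a summary and not a full specification. For Aim 3 the same section lists the model's terms explicitly, and for Aim 1 it does not, so the analyst may have intended more. That is fair as to intent, but nothing given for Aim 1 implies cadence or volume terms, and a plan is read for what it commits to. It is also true that fits by condition could answer the objective, but none is planned.

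A second reply is that little is at stake: a mechanistic aim with 20 patients and one visit, already completed. This stands as a limit on the consequence. The Aim 2 and Aim 3 models do not depend on this one.

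A third reply also stands. Section VI does not say that each liner and the gel pad were run at every vacuum setting and cadence, or that condition was recorded per trial. The visit took place at the manufacturer's site. Section V says that this site has its own approved protocol for its part of recruitment and visits, and that protocol is not in the documents. If volume conditions were run at one setting only, an exposure-by-volume effect may still be estimable, but a setting-by-volume effect is not.

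A reader might infer that the design cannot answer Aim 1, or that 20 patients give some particular power for the interactions. The documents support neither. The conditions vary within patient, and the gap is in the written analysis. Any power figure would need the numbers of cadences and liners, the slopes, the standard deviations and the between-patient variation in the interactions, none of which is given.

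**Conclusion.** The concern holds in this form: run as written, the stated Aim 1 model omits two of the three named modifiers and all three interactions. It therefore yields one pooled slope per outcome and no estimate or interval for the second half of the objective. This follows from the text alone and rests on no assumed figure.

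Three stronger statements should not be drawn from it:

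- Vacuum pressure is not missing from the model. It is there as an adjustment, and for that factor only the interaction is absent.
- The documents do not show that the analysis actually done lacked these terms. They show only what was planned.
- A re-analysis is not guaranteed to recover every interaction, because the crossing and the recording of conditions are not stated.

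The plan should be corrected, but the reach is limited to Aim 1.

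**What to change.** 1. Define wave amplitude and state which variable is the vacuum-pressure exposure.
2. Keep the planned random-effects model and covariates, fitted separately for distal movement and lateral shift, with vacuum setting retained.
3. Add cadence and volume condition (liner thickness, gel pad) as fixed effects. State that cadence is the recorded proxy for gait speed, since speed also depends on step length.
4. Add exposure-by-setting, exposure-by-cadence and exposure-by-volume interactions wherever the recorded conditions allow. Where conditions were not crossed, say which interaction cannot be estimated.
5. If wave amplitude is not a measure of vacuum pressure, fit movement on vacuum setting with setting-by-cadence and setting-by-volume terms, under the same proviso.
6. Where the data allow, let the exposure slope vary by patient, so that the interaction intervals are not too narrow.
7. Report the interaction estimates with intervals as the main result, and label the analysis post hoc if results have been seen.

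No new patients or visits are needed, provided condition was recorded for each trial. The costs are wider intervals and a larger Holm family. If each modifier also gets one joint test, three modifiers and two outcomes add 3 × 2 = 6 tests. The smallest p-value would then have to pass 0.05 / 6 = 0.0083 if Holm covered those alone, and a stricter level within the wider family that the plan implies. With 20 patients, the intervals will probably be more informative than the tests.

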4. At least 3 months post-amputation per physician discretion
5. Residual limb length greater than 6.5 inches in length
6. Able to follow directions and give informed consent on their own or through Legally Authorized Representative.
7. Must be able to ambulate without assistance. An external assistance device such as cane or walker will be permitted.
8. Adequate arterial blood flow of the index stump as evidenced by TcOM > 30 mmHG, measured within the past 12 months.

IV. Exclusion Criteria:

1. Conditions that prevent wearing a prosthetic socket; such as existing scab, ulcer, or keloid scar on amputation stump.
2. Cognitive deficits or mental health problems that would limit ability to consent and participate fully in the study protocol
3. Women who are pregnant or who plan to become pregnant in the near future

V. Study Design:

This study has 3 aims where trans-femoral and trans-tibial amputees will be enrolled.

Subjects enrolled in Aim 1 (N=20) will have one study visit that will take place at The Ohio Willow Wood (OWW).

Subjects enrolled in Aim 2 (N=30) will have a total of 4 visits at baseline, month 1, month 2, and month 3.

Subjects in Aim 3 (120) will be enrolled at Indiana University (n=30 subjects), OWW (n=30), and at Walter Reed National Military Medical Center (WRNMMC) (n=60 subjects) with a total of 3 visits at 0 week (baseline), 0-4 weeks (socket fitting visits), and 16 weeks (final visit).. OWW and Walter Reed National Military Medical Center (WRNMMC) have separate IRB protocol & approval to conduct their part of subject recruitment and study visits. Aims 2 and 3 will not be run concurrently. Subjects enrolled in Aim 2 can participate in Aim 3. Aim 2 studies performed at Ohio State and Indiana University. Aim 2 has enrolled 15 subjects through Ohio State University & OWW (and these 20 subjects have completed their participation in the study) and the data is currently being analyzed to determine if additional subjects are required. If analysis shows sufficient subjects have been enrolled to achieve the study aim, no additional subjects will be enrolled in Aim 2. If there is insufficient data, the remainder of the Aim 2 subjects will be enrolled through OWW under their approved IRB with WIRB. Aim 3 studies performed at IU, OWW and WRNMMC per their approved IRB protocols. The vacuum suspension used for the study is new to all enrolled subjects

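### Aim 2's only planned analysis compares adaptive EVS with suction at 12 weeks, but the Aim 2 visits describe no suction condition, and the model has no term for socket movement, which is the Aim 2 question

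*Combined protocol and SAP*

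**What the plan says.** Section II states the question: "Aim 2 will evaluate the impact of socket movement on residual limb circulation and residual limb skin health". Section VII repeats, at every Aim 2 visit, that the data serve to show how socket movement affects limb health.

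Section VII gives the visits. At visit 1 the prosthetist sets a first vacuum level, and at visits 2 and 3 (months 1 and 2) the next level. None is set at visit 4 (month 3), and only at the end of that visit do subjects go back to their standard-of-care prosthesis. No visit names a suction socket or lists a motion measurement. Section V adds: "The vacuum suspension used for the study is new to all enrolled subjects".

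Section XV gives the Aim 2 analysis, a random-effects linear regression to "compare percent change in limb perfusion across adaptive EVS and suction at 12 weeks controlling vacuum pressure", also "controlling for the baseline EVS and suction values". Age, diabetes status and smoking history enter every model.

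The platform descriptions in Section V define suction as "A total contact weight bearing socket with a one-way expulsion valve to let air out". They say that the adaptive system "automatically detects the socket fit based on in-socket motion".

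On progress, Section V says that "the data is currently being analyzed to determine if additional subjects are required". It gives two counts for the subjects already in: "Aim 2 has enrolled 15 subjects through Ohio State University & OWW (and these 20 subjects have completed" their participation.

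**The concern.** The analysis section and the visit schedule describe different studies. One compares two suspension types at 12 weeks. The other moves every subject through vacuum levels and asks about movement inside the socket. In the Section II objectives, suction is a comparator for Aim 3, not for Aim 2.

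If Section XV is followed on the visits as described, statistical software will drop the suspension term. What remains is a coefficient for vacuum pressure, which the plan treats as an adjustment variable and not as the effect of interest. Any reported Aim 2 result would then rest on a choice that the plan does not make. Aim 2 data are already being examined to decide whether to enrol more subjects, and the document does not say by which analysis. A replacement chosen after seeing those data is open to bias, and more subjects would not make the stated contrast estimable.

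**Working it through.** The documents give no effect size, standard deviation or power for Aim 2, so there is no stated figure to reproduce. The check is whether the stated coefficient can be estimated.

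**Inputs**
- Planned N: 15 + 15 = 30 (Section II). Enrolled so far: 15 or 20 (Section V).
- Time point: 3 months is 3 × 365.25/12/7 = 13.0 weeks, so the 12-week value is taken to be visit 4.
- Fixed-effect columns (Section XV): intercept, EVS versus suction, vacuum pressure, baseline, age, diabetes, smoking. That makes 7, or 8 if separate EVS and suction baselines are entered as the text literally reads.
- Assumption: three distinct vacuum levels with placeholder values, because Section VII gives none.

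**Week 12 as described.** Nobody is measured in suction: 0 of 30, 0 of 20 or 0 of 15. The group column equals 1 for every subject, which is the intercept column. One column is lost, so the rank is 7 − 1 = 6. If everyone also has the same vacuum pressure at week 12, that column is constant too and the rank is 7 − 2 = 5.

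| Rows used | Vacuum pressure | Rank, 7 columns | EVS versus suction |
|---|---|---|---|
| Week 12 | differs between subjects | 6 | not estimable |
| Week 12 | same for all | 5 | not estimable |
| Months 1-3 stacked | differs between visits | 6 | not estimable |

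With 8 columns the week-12 ranks are 7 and 6. All these ranks are the same at n = 15, 20 and 30. In the stacked case the vacuum-pressure coefficient is estimable and the group coefficient is not.

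**If a pump-off level counted as suction (illustration).** Aim 1 used settings of 0, 7, 10, 13 and 20 inHg; whether Aim 2 did is not stated. Take equal numbers of visits at 0 and at two non-zero settings, and regress group on pressure.
- Settings 0, 7, 20: mean pressure 9. The group-pressure cross-product is 9, the group sum of squares is 2/3 and the pressure sum of squares is 81 + 4 + 121 = 206. R² = 81/(2/3 × 206) = 0.59, and the variance inflation factor is 1/(1 − 0.59) = 2.4.
- Settings 0, 10, 13: the same steps give R² = 0.95 and an inflation factor of 20.6.

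Stacked over months 1-3 the model then has full rank (7 of 7), but adjustment for pressure takes out 59% to 95% of the variation in the group term. If all subjects had the same level order, everyone is in the same condition at week 12. The rank is then 5 of 7, and removing vacuum pressure leaves 5 of 6. The week-12 contrast is still not estimable.

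**Exposure.** Section II names socket movement. The Section XV columns contain no movement variable. Vacuum pressure is at most a proxy for it and is entered only to be adjusted away.

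**The case against.** Four arguments carry weight.

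1. *A suction condition may be described elsewhere.* Any further Aim 2 subjects would be enrolled at OWW under a separately approved protocol that is not among these documents. This stands as a limit. A reader might infer that Aim 2 has no suction data at all; the documents show only that none are described here.

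2. *Visit 1 may have been in suction.* The vacuum-setting step is listed after the skin measurements, and the device is new to all subjects, so some may have been measured in their own suction prosthesis. Measurements are taken before and after activity, so percent change could mean the response to activity, which would make visit 1 an outcome row. If visit-1 rows count as suction, the rank is 7 of 7 (assumed levels 0, 10, 13 and 20). That contrast could be fitted, but it would be confounded with time and would not be the stated 12-week comparison.

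3. *Pressure is not a fixed constant.* The device adjusts vacuum itself, so recorded pressure may vary between subjects at one setting. If so, the week-12 rank is 6, not 5, and the shared-variance figures change. The group term is still not estimable while nobody is in suction.

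4. *The data remain analysable and overseen.* The vacuum coefficient can be estimated from the stacked visits, and under Section XIII a DSMB that includes a statistician meets after the first 15 Aim 2 subjects. So it would be too strong to say that Aim 2 cannot be analysed. Oversight, however, does not prespecify an analysis.

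It is also tempting to say that every collected skin measure must become a confirmatory outcome. The documents do not require that. The lack of a planned Aim 2 analysis for TEWL and capacitance is mainly missing detail.

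**Conclusion.** The point holds and must be fixed in two respects: the suction contradiction and the exposure mismatch.

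On these documents the 12-week EVS-versus-suction coefficient is not estimable at any sample size (rank 6 of 7, or 5 of 7 with common vacuum pressure). This rests on reading visit 4 as week 12 and on the absence of any described suction measurement there; it does not depend on the placeholder vacuum levels. Separately, even a fitted version of the model would not answer the Aim 2 question, because it has no movement term.

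The 59% to 95% range and the ranks for a pump-off level borrow Aim 1's settings and are illustrative only. A reader might also take a pump-off EVS socket to be suction; the documents do not show that it meets Section V's expulsion-valve definition.

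**What to change.** 1. **Reconcile** Sections II, V, VII and XV and the OWW protocol. State the socket and vacuum condition at each Aim 2 visit, including the socket worn for the visit-1 measurements.

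2. **If no suction condition with its timing and baseline is documented**, delete the EVS-versus-suction contrast from Aim 2. Replace it with a random-effects model (patient as random term) of perfusion at months 1-3, adjusted for the visit-1 value, age, diabetes and smoking. The exposure is recorded in-socket motion if it was logged, otherwise the vacuum level worn since the previous visit. With three levels as two indicators, this model has full rank (7 of 7). If only vacuum level is available, limit the conclusions to vacuum level. If all subjects had the same level order, state that level and time cannot be separated: adding month as a category then gives rank 7 of 9, against 9 of 9 when the order varies.

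3. **If a documented condition is accepted as suction**, keep the contrast without vacuum pressure as a covariate, and use all visits at which each condition was worn rather than week 12 alone.

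4. **Skin-health measures.** Apply the same model to those already collected, and state whether they are confirmatory under Holm or descriptive. That is the sponsor's choice.

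5. **Timing.** Make the change before Aim 2 data are used to decide on enrolment. Report that it was written after 15 or 20 subjects had completed, and resolve which count is correct.

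**Cost.** An SAP amendment and a records check. Aim 2 loses its suction claim unless a suction condition is documented, and without logged motion it speaks to movement only indirectly. If all six listed measures were made confirmatory with one joint test each, the first Holm threshold within Aim 2 would be 0.05/6 = 0.0083. It would be smaller if the family covers the whole study.
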